Study design: This retrospective physician based medical record review will collect data from medical records of patients, who have received palbociclib combination therapy as first line treatment for ABC/MBC, across 7 countries in Latin America. Data collection in 6 countries has already been conducted: Chile, Argentina, Peru, Mexico, Costa Rica, and Panama. In countries where palbociclib has been on the market for a sufficient period of time and therefore sufficient follow-up data are available, a one-time review of patient's medical records will be conducted.

Population: Data will be collected from Colombia with approximately 30-40 oncologists or gynecologists recruited. To be eligible to participate physicians must have treated or be treating 4 or more HR+/HER2- ABC/MBC patients with palbociclib combination therapy in the first line setting. Each physician will complete up to 8 electronic case report forms (eCRFs). Previously data has been collected in Chile (1 oncologist providing 8 eCRFs, Argentina (41/469), Peru (5/30), Mexico (15/99) and Costa Rica (6/35) and Panama (1/6).

Recruited physicians must go back in their records to the specific index date and select the next 'n' number of eligible patients for which they will complete eCRFs. The 'index date' will be defined as 60 days after the physician first prescribed palbociclib + partner therapy following the availability of specific indication in the market. To be eligible, patients must be female, aged 18 or over, have been diagnosed with HR+/HER2- ABC/ MBC and must have received palbociclib combination as a first line therapy. They also must have a minimum of six months follow up data since palbociclib + aromatase inhibitor initiation and three months follow up data for palbociclib + fulvestrant initiation.

It is expected that approximately 30-40 physicians will be recruited in Colombia to complete 200 eCRFs, combined and with previous data collection in Chile, Argentina, Peru, Mexico, Costa Rica and Panama, it is expected that approximately 99-109 physicians will be recruited in total, this will enable data to be collected for approximately 790-890 patients overall across Latin America.

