Variables: The variables assessed in this study will be patient demographics at the time of data collection, clinical characteristics, comorbid conditions, early and advanced breast cancer treatment history, palbociclib treatment patterns including dose changes, clinical outcomes and time since deceased (no. of days) if applicable.

Data sources: Patient medical records will be used as the data source.

Study size: Approximately 30-40 physicians will be recruited in Colombia collecting data for approximately 200 patients. In Argentina, Mexico, Costa Rica, Panama, Peru and Chile, 69 physicians were recruited overall, which enabled data to be collected for 647 patients. This sample is in addition to that previously collected in Argentina in wave 1 Global IRIS (162 patient records were collected from 41 physicians, protocol no. A5481090). In Mexico, 15 physicians were recruited collecting 99 eCRFs. Five physicians in Peru collected 30 eCRFs. A total of 7 physicians were recruited across Costa Rica and Panama with a sum of 41 CRFs. In Chile 1 physician was recruited collecting a total of 8 eCRFs.

Data analysis: All analyses will be descriptive in nature. Categorical variables will be described using the number of observations and number and percent (%) in each category. Numeric variables will be described using the number of observations, mean and standard deviation, and minimum, maximum, median and interquartile range. Time to event will be described using a Kaplan-Meier chart or the median.

Milestones: The medical record review data collection began in June 2019 and was completed by September 2019 for Argentina, Mexico, Costa Rica, Panama, Peru and Chile. Medical record review collection for Colombia is due to begin August 2020 and should be completed by October 2020; however this will depend upon market approval dates and the required follow-up time for outcomes evidence. Following completion of data collection in all markets, the final study report will be written and completed by December 2020.

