8. RESEARCH METHODS

8.1. Study Design

This study will be conducted as a retrospective medical record review of patients who have received palbociclib combination treatments as first line treatment regardless of combination partner and labelled use. Upon completion, the study will comprise of a medical record review conducted in Argentina, Chile, Peru, Mexico, Colombia and a combined sample in Costa Rica and Panama. Data collect for Argentina, Chile, Peru, Mexico, Panama and Costa Rica were completed in September 2019, data collection for Colombia is due in August 2020. The study design is outlined in [Figure 1](#). The study design is similar to the IRIS Global study previously conducted (protocol no. A5481090).^{10,11}

Data collection will be online via electronic data capture using electronic case report form (eCRF). In Colombia eligible physicians will be invited to complete an eCRF for between 6-8 patients that meet the study criteria. Each eCRF will take around 25 minutes to complete. Patient eligibility will be confirmed by treating physicians. In order to allow for a sufficiently long observational window, treating physicians will be asked to go back to a specific point in time, the index date, and sequentially select the medical records of the next 'n' patients who meet the inclusion criteria. The 'index date' will be defined as 60 days after the physician first prescribed palbociclib + partner therapy following the availability of specific indication in the market (eg, If palbociclib + letrozole was available Dec 14, 2015 in Argentina and the physician initiated a patient on palbociclib+ letrozole the next day, the index date will be Feb 12, 2015). The index date will differ for the specific indications/combination partners if approved on different dates. Approval dates can be found in [Section 6](#).

[figure not shown]

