8.2. Setting

Upon study completion data will be collected from 7 countries. Approximately 30-40 physicians will be recruited in Colombia. Data will be collected retrospectively at a single point in time from patient medical records. To date, 6 physicians in Costa Rica, 1 in Panama, 1 in Chile, 15 in Mexico, 41 in Argentina and 5 in Peru completed eCRFs.

Screening questions/recruitment criteria will ensure the relevant physicians are selected and all other non-qualifying physicians will be excluded. In addition, a representative geographical split and private/public practice split for physicians will be sought where possible to ensure a representative sample.

To be eligible, physicians must have treated or be treating four or more HR+/HER2- ABC/MBC patients who meet the eligibility criteria for the study. This will ensure that recruited physicians will be able to complete the minimum number of eCRFs required to participate in the study. Once physicians have been recruited, they must go back to a specific index date, defined in [Section 7.1](#), and select the next 'n' number of eligible patient records from patients who have been treated with a palbociclib combination. The consecutive approach to recruitment will be stressed to each participating physician to limit selection bias. Physicians will confirm patient eligibility.

Patient records must meet the following criteria to be eligible for the medical record reviews. They must be female, over 18 years of age and they must have been diagnosed with HR+/HER2- ABC/MBC. Patients must have received palbociclib as a first line therapy. For the chart review, palbociclib and letrozole/aromatase inhibitor must have been initiated a minimum of 6 months prior to date of medical chart review, and palbociclib and fulvestrant must have been initiated a minimum of 3 months prior to date of medical chart review. This will permit the capture of meaningful clinical outcomes data.

A full list of the eligibility criteria can be found in [Section 8.2.1](#).

In order to ensure that sufficient data is captured for each indication, indication quotas will be enforced. This will be determined on a country by country basis.

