8.2.1. Inclusion Criteria

Physician inclusion criteria:

- Oncologist or gynecologist.
- Responsible for treating $\geq 4-10$ (depending on country) ABC/MBC patients who meet the eligibility criteria.
- Agrees to participate in the study and complete the CRFs within the data collection period.

Patient inclusion criteria:

- ≥ 18 years old.
- HR+/HER2- breast cancer diagnosis with confirmed metastatic or advanced disease.
- Received palbociclib as a first line therapy.
- No prior or current enrolment in an interventional clinical trial for ABC/MBC.
- Minimum of three months of follow up data since palbociclib with fulvestrant initiation, or minimum of six months of follow up data since palbociclib with letrozole/aromatase inhibitor initiation.

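### The follow-up eligibility rule is worded in two conflicting ways; if section 8.2.1 is applied literally, early deaths are excluded and 1- and 2-year survival is biased upward

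*Combined protocol and SAP*

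**What the plan says.** The protocol states the rule in two forms.

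- **Follow-up data.** Section 8.2.1 lists among the patient criteria a "minimum of six months of follow up data since palbociclib with letrozole/aromatase inhibitor initiation", or three months for fulvestrant. The abstract (Population) agrees: "They also must have a minimum of six months follow up data since palbociclib + aromatase inhibitor initiation", again with three months for fulvestrant.
- **Calendar time.** Section 8.2 says that "palbociclib and letrozole/aromatase inhibitor must have been initiated a minimum of 6 months prior to date of medical chart review", with 3 months for fulvestrant. It sets no condition on vital status or on how long the record runs.

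Section 8.2 then adds "A full list of the eligibility criteria can be found in" section 8.2.1. The section with the calendar wording therefore points to the section with the follow-up-data wording as the complete list.

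The affected outcome is in section 7.1: the proportions alive 1 and 2 years after palbociclib initiation fall under a primary objective, subject to available follow-up. Section 8.7 plans Kaplan-Meier description with 1- and 2-year rates and mentions neither a landmark nor delayed entry. Under section 8.2 physicians confirm eligibility themselves, and section 8.9 provides for no monitoring visits and no source data verification.

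**The concern.** The two wordings part company for patients who die, or whose record stops, inside the window. Someone who started palbociclib plus an AI two years before review and died in month 4 is eligible under section 8.2. Under section 8.2.1 read literally she is not, because she has only four months of follow-up data. Nothing says that death completes follow-up.

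If the literal rule is used, every patient analysed has survived to month 6 (AI) or month 3 (fulvestrant) by construction, yet the clock still starts at initiation. The survival curve then has a built-in stretch without deaths. AI and fulvestrant patients would also be conditioned on different survival times, which makes their results hard to set side by side. Because physicians apply the rule themselves without verification, two physicians could read it differently and nobody would notice. Section 8.10 does not list this among the limitations. A later analysis plan could relabel the estimates but could not recover patients who were never selected.

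**Working it through.** The documents give no survival assumption or early death rate, so there is no plan figure to reproduce. The record count does reproduce: 469 + 99 + 8 + 41 + 30 = 647 completed records (section 8.5, Table 2), and 647 + 200 = 847 with Colombia.

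**Inputs.** Minimum follow-up L = 6 months (AI) or 3 months (fulvestrant), from section 8.2.1. Time zero is initiation, from section 7.1. Assumption: a proportion q is dead by month 6, with q = 1%, 2% or 5%, and the hazard is constant, so S(t) = (1 − q)^(t/6) with t in months. Loss to follow-up is taken as unrelated to death.

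**Formula.** Under section 8.2 the Kaplan-Meier estimate targets S(t). If entry requires follow-up to L, it targets S(t)/S(L), which is never below S(t). The relative inflation is 1/S(L).

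- AI rule: S(12) = (1 − q)² becomes (1 − q); S(24) = (1 − q)⁴ becomes (1 − q)³.
- Fulvestrant rule: S(12) becomes (1 − q)^1.5; S(24) becomes (1 − q)^3.5.

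| q | 1-year: S(t) | 1-year, AI rule | 1-year, fulvestrant rule | 2-year: S(t) | 2-year, AI rule |
|---|---|---|---|---|---|
| 1% | 98.0% | 99.0% (+1.0) | 98.5% (+0.5) | 96.1% | 97.0% (+1.0) |
| 2% | 96.0% | 98.0% (+2.0) | 97.0% (+1.0) | 92.2% | 94.1% (+1.9) |
| 5% | 90.3% | 95.0% (+4.8) | 92.6% (+2.3) | 81.5% | 85.7% (+4.3) |

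Differences are taken before rounding. For scale, the simple binomial 95% half-width for 1-year survival with 847 patients is 1.96 × √(S(1 − S)/847), or 0.9, 1.3 and 2.0 points in the three rows. If all patients were on an AI, the bias would be at least about that large; censoring would widen the interval.

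**Progression-free proportions.** The effect depends on how death is handled, which section 8.3 (Table 1) does not define. As an illustration, take the 24.8-month median from section 6 with an exponential curve.

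- *Death is an event.* The 12-month figure is 0.5^(12/24.8) = 71.5%. Dividing by 1 − q gives 72.2%, 73.0% and 75.3%.
- *Death is censored, q = 5%.* There are three cases.
  - Early deaths only after progression: 71.5% becomes 75.3%, the full factor 1/0.95.
  - Death independent of progression: no change.
  - Early deaths only before progression: the estimate falls slightly. The progression hazard is h = ln 2/24.8 = 0.02795 per month. The death hazard m that solves [m/(h + m)] × [1 − exp(−6(h + m))] = 0.05 is m = 0.0093. Among those alive at month 6, exp(−6(h + m))/0.95 = 84.2% are progression-free, against exp(−6h) = 84.6%. At months 12 and 18 the figures are 71.2% against 71.5% and 60.2% against 60.5%.

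**The case against.** The strongest reply is that the calendar reading is what the sponsor meant. The abstract ties adequate follow-up to time on the market ("sufficient period of time and therefore sufficient follow-up data are available"), and its milestones tie timing to approval ("this will depend upon market approval dates and the required follow-up time for outcomes evidence"). Section 8.1 explains the index date as a means "In order to allow for a sufficiently long observational window". Data come from a single review, so follow-up since initiation can naturally mean time from initiation to review. Section 8.2.1 also leaves out the requirement that patients be female, so it has to be read together with section 8.2. All of this stands: the calendar reading is at least as plausible as the literal one, and under it there is no bias. It does not settle the matter, because the stricter wording appears twice and is called the full list. The abstract also lists "time since deceased (no. of days) if applicable" as a variable, but that shows only that deaths are recorded, not that early deaths qualify.

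It is also fair to say that the size is not anchored. The only survival figure in the documents, 22% at 5 years for metastatic disease in general (section 6), implies 1 − 0.22^0.1 = 14% dead by month 6 at a constant hazard. That is outside the 1% to 5% range and would raise 1-year survival from 73.9% to 85.9% under the AI rule. It describes a different population, so neither range should be relied on. Survival reporting is itself conditional on available follow-up, and the study is descriptive.

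Three stronger inferences should be resisted.

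- A reader might infer that the 647 completed records are already biased, or were screened differently from Colombia. Nothing shows this; the only change logged for the current version is the addition of Colombia.
- A reader might infer from section 8.10 that the follow-up minimum is left to the CRFs. That sentence concerns the systematic patient selection criteria and approval dates, not the minimum.
- A reader might infer that progression-free results must also be inflated. If deaths are censored, the sign can reverse.

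**Conclusion.** The conflict in wording is real and bears on a primary outcome. The calendar wording gives no bias. Section 8.2.1 applied literally biases 1- and 2-year survival upward by the factor 1/S(6) or 1/S(3); the direction is certain, the size is not. With an assumed 1% to 5% dead by month 6 and a constant hazard, 2-year survival rises by about 1.0 to 4.3 points under the AI rule, alongside the 1-year shifts in the table. Progression-free proportions rise by the same factor if death is an event. If deaths are censored, the effect runs from a slight decrease, through none, to that factor. Which rule was used in 2019 cannot be told from the documents, so this is an ambiguity to resolve and not evidence that any result is biased.

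**What to change.** 1. Change the abstract and section 8.2.1 to the section 8.2 rule: treatment initiated at least 6 months (AI) or 3 months (fulvestrant) before the date of chart review. Add that this applies regardless of whether the patient has since died, progressed or been lost to follow-up. Use the same text in the Colombia screener before collection starts.
2. State in section 8.3 whether death is an event in the progression-free proportion.
3. Check which wording the 2019 screener used for the 647 records. A count of deaths before month 6 (AI) or month 3 (fulvestrant) is a cheap cross-check: any such death shows that the literal rule was not applied throughout. Finding none is less clear-cut. The partner split is not given; treating all records as AI or all as fulvestrant, and patients as independent, the chance of no such death under the calendar rule at 2% six-month mortality is 0.98^647 = 0.000002 or 0.98^323.5 = 0.0015. At 0.5% it is 0.039 or 0.198, so an empty count would not be decisive.
4. Only if the 2019 screener required follow-up data: label those survival and PFS results as conditional on follow-up to month 6 or 3, show them separately from Colombia, and say so in section 8.10.

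The cost is small: a wording change in two places and in one screener, one definition, one look at the 2019 screener and one count in data already held. No extra patients or new methods are needed.

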8.2.2. Exclusion Criteria

Physician exclusion criteria:

- Qualified less than 2 years ago or more than 35 years ago.
- Participated in observational research for ABC/MBC in the last 3 months.
- Have not prescribed either palbociclib plus fulvestrant or palbociclib plus aromatase inhibitor as first line therapy.

8.3. Variables

Table 1. List of Study Variables

Variable	Role	Data Source(s)	Operational Definition
Patient demographics	Baseline Sub-group identifier	Patient records	Age, ethnicity, weight, height, biomarker status, family history of breast cancer.
Clinical characteristics	Baseline Sub-group identifier	Patient records	Time since diagnosis, staging, node status, menopause status. ECOG/Karnofsky functional status, diagnosis for which palbociclib combination was prescribed, sites of metastases, de novo vs. recurrent disease.
Comorbid conditions	Baseline	Patient records	Comorbid conditions.
Early treatment history	Baseline Sub-group identifier	Patient records	Adjuvant treatments received since breast cancer diagnosis. Time since end of adjuvant treatment. Surgery/radiotherapy received.

Variable	Role	Data Source(s)	Operational Definition
Advanced treatment history	Baseline Sub-group identifier	Patient records	Treatments and supportive therapies received since metastatic/advanced HR+/HER2- diagnosis. Duration of treatments. Reasons for regimen changes.
Palbociclib combination treatment	Exposure Sub-group identifier	Patient records	Starting dose, duration of treatment, changes in dose, interruptions, cycle delays and discontinuations. Where possible reasons for change in treatment.
Clinical outcomes	Outcomes	Patient records	Proportion progression free, ORR, TTP, PFS, 1-yr and 2-yr survival in all patients and within specific subgroups.

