**TREATMENT PATTERNS AND CLINICAL OUTCOMES AMONG PATIENTS IN
LATIN AMERICA RECEIVING FIRST LINE PALBOCICLIB COMBINATIONS
FOR HORMONE RECEPTOR POSITIVE/ HUMAN EPIDERMAL GROWTH
FACTOR RECEPTOR 2 NEGATIVE (HR+/HER2-) ADVANCED/METASTATIC
BREAST CANCER IN REAL WORLD SETTINGS**

This document contains confidential information belonging to Pfizer. Except as otherwise agreed to in writing, by accepting or reviewing this document, you agree to hold this information in confidence and not copy or disclose it to others (except where required by applicable law) or use it for unauthorized purposes. In the event of any actual or suspected breach of this obligation, Pfizer must be promptly notified.

Study Information

Title	Treatment Patterns and Clinical Outcomes Among Patients in Latin America Receiving First Line Palbociclib Combinations For hormone receptor positive/ human epidermal growth factor receptor 2 negative (HR+/HER2-) Advanced/Metastatic Breast Cancer in Real World Settings.
Protocol number	A5481125
Protocol version identifier	Version 3.0
Date	13 August 2020
Date of last version of protocol	16 April 2019
Active substance	L01XE33 - Palbociclib
Medicinal product	Ibrance (palbociclib)
Research question and objectives	To describe patient demographics, clinical characteristics, treatment patterns and clinical outcomes of adult female patients who have received palbociclib combination treatments as first line therapy, regardless of combination partner and labelled use in real world settings across Latin America.
Primary objectives	
To describe demographics and clinical characteristics of patients who have received palbociclib combination treatment as a first line therapy, regardless of combination partner and labelled use.	
To describe adjuvant therapies received for the treatment of early or locally advanced breast cancer (Stages 0-IIIa).	
To describe treatments received in the advanced/metastatic setting, before and after palbociclib combination use.	
To describe dosing and dose changes, interruptions, and delays associated with palbociclib use in clinical practice.	

To detail supportive therapies received by patients while receiving palbociclib combination treatment.

To determine in overall population and defined subgroups, clinical outcomes including.

Proportion of patients who are progression free at specific intervals (eg, 6, 12, 18 months).

Objective response rate (ORR).

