7.1. Primary Objectives

- To describe the demographic and clinical characteristics of patients who have received palbociclib combination treatments as first line treatment, regardless of combination partner and labelled use.
- To summarize adjuvant therapies received for the treatment of early or locally advanced breast cancer (Stages 0-IIIa).
- To describe treatments received in the advanced/metastatic setting, before and after palbociclib combination use.
- To describe dosing and dose changes, interruptions, delays, and discontinuations associated with palbociclib use in clinical practice.
- To describe supportive therapies received by patients while receiving palbociclib combination treatments.
- To determine clinical outcomes including (but not limited to).
 - Proportion of patients who are progression free at multiple intervals (eg, 12, 18 months).
 - Objective response rate (ORR) - depending on availability of follow-up data.
 - Proportion of patients alive 1- and 2-year post palbociclib combination initiation - depending on availability of follow-up data.

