8.7. Data Analysis

Detailed methodology for summary and statistical analyses of data collected in this study will be documented in a Statistical Analysis Plan (SAP), which will be dated, filed and maintained by the sponsor. The SAP may modify the plans outlined in the protocol; any major modifications of primary endpoint definitions or their analyses would be reflected in a protocol amendment.

All analyses are to be descriptive and so all methods to be used will reflect this descriptive nature. The specific method that will be used depends on type of variable being analyzed and those methods are:

- Categorical variables – will be described using:
 - Number of observations (n);
 - Number and percent (%) within each category;
 - Number of missing observations.
- Numeric variables – will be described using:
 - Number of observations (n);
 - Mean & Standard deviation;
 - Minimum, Maximum, Median and 1st & 3rd Quartiles;
 - Number of missing observations.
- Time to event – will be described using:
 - A Kaplan-Meier chart that will visually estimate the distribution of times to some events, eg, progression, and will take into account those patients for which the event has not as yet occurred;

- 1-yr and 2-yr rates, median or some more appropriate percentiles if the median time is not reached in the sample.

The analyses will be conducted (using the methods above) in a number of phases, as already detailed in the [Study Design](#) section.

Missing data will be excluded on a case by case basis and will not be imputed. This will mean that each table will not necessarily be based on the same number of patients.

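### Table 1 lets post-start palbociclib events define outcome subgroups, with no baseline rule or landmark; splits made that way would be biased

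*Combined protocol and SAP*

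**What the plan says.** In section 8.3, Table 1, the palbociclib combination treatment row has the role "Exposure Sub-group identifier". Its operational definition is "Starting dose, duration of treatment, changes in dose, interruptions, cycle delays and discontinuations", plus reasons for change where possible. The clinical outcomes row of the same table reads "Proportion progression free, ORR, TTP, PFS, 1-yr and 2-yr survival in all patients and within specific subgroups". The Study Information table at the front of the protocol puts subgroups into a primary objective: "To determine in overall population and defined subgroups, clinical outcomes including". Section 7.1 lists the same outcomes without the subgroup clause.

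The advanced treatment history row is labelled as a baseline variable and a sub-group identifier. It is defined as "Treatments and supportive therapies received since metastatic/advanced HR+/HER2- diagnosis. Duration of treatments". Section 7.1 shows that this information does not stop at palbociclib start: "To describe treatments received in the advanced/metastatic setting, before and after palbociclib combination use" and "To describe supportive therapies received by patients while receiving palbociclib combination treatments".

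For time-to-event data, section 8.7 plans "A Kaplan-Meier chart that will visually estimate the distribution of times to some events", allowing for patients without an event, and leaves detailed methods to a separate SAP. Section 8.8 describes exploratory, descriptive stratifications, including responders against non-responders by best recorded response, and possibly country. Neither section says when subgroup membership is fixed.

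**The concern.** A Kaplan-Meier curve counted from treatment start is interpretable by subgroup only if membership is known at the start. A patient enters a dose-change, interruption or delay group only by staying progression-free and under observation until that event. Patients who progress early fall into the unchanged group by construction. The changed group then looks better even when the change has no bearing on outcome.

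Duration and discontinuation have a further problem. Progression itself ends treatment, so the outcome helps to define the group, and the distortion may run in the opposite direction. The same holds for advanced treatment history where it includes therapy given during or after palbociclib.

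Calling the analysis descriptive removes the tests but not the bias in the displayed curves and percentages. Section 6 says the results should help inform treatment decisions, and section 11 foresees publication. A false advantage for patients with dose changes could be read as a clinical message.

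**Working it through.** The plan gives no figure to reproduce, since sample size and testing are explicitly not used. The check asks how large a false gap appears when the true effect is nil.

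**Inputs from the protocol**
- Median PFS of 24.8 months (letrozole combination) and 10.8 months (fulvestrant combination), section 6.
- Minimum follow-up of 6 months (letrozole or aromatase inhibitor) and 3 months (fulvestrant), section 8.2.1.
- Longest windows, if first prescribed on availability, from availability plus 60 days. Colombia, November 2018 to end October 2020: about 21 months. Argentina to 30 September 2019: 43.6 months for letrozole (14 December 2015) and 35.5 months for fulvestrant (16 August 2016).

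**Assumptions.** PFS is exponential and dose change is independent of PFS. Follow-up is uniform from the minimum to 21 months, to a middle case of 36 months, or to the longest Argentina window for that partner. The share and timing of dose changes are assumed, because the protocol gives neither.

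**One scenario by hand.** The median is 24.8 months, 20% of patients are due a change, and its timing is uniform over months 0.5 to 3.
- Rate: λ = ln 2 / 24.8 = 0.02795. True 12-month value: S(12) = 2^(−12/24.8) = 71.5%.
- Probability of being progression-free when the change falls due: q = (e^(−0.5λ) − e^(−3λ)) / (2.5λ) = (0.9861 − 0.9196) / 0.0699 = 0.952.
- Changed group: S(12)/q = 0.715/0.952 = 75.1%.
- Unchanged group: 0.8 × 0.715 / (1 − 0.2 × 0.952) = 0.572/0.810 = 70.7%.
- False gap: 4.4 points. With 40% due a change, the unchanged group is 0.6 × 0.715 / (1 − 0.4 × 0.952) = 69.3%, and the gap is 5.8 points.

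**All scenarios** (simulation, at least 1,000,000 patients each; naive Kaplan-Meier at 12 months; changed minus unchanged, percentage points)

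| Assumed timing of first change | Median 24.8 (true 71.5%) | Median 10.8 (true 46.3%) |
|---|---|---|
| Months 0.5–3, 20–40% due a change | 4–6 | 6–9 |
| Months 1–8, 20–40% | 11–15 | 17–21 |
| Months 1–12, 20–40% | 15–20 | 24–29 |
| Constant rate, mean 24 months | 21–31 | 28–36 |

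These are illustrations, not bounds. A separate model assumed 35% with a change by month 6 and follow-up cut at 24 months. At the 24.8-month median it gave 86.4% against 43.4% at 12 months, a gap of 43 points.

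**Landmark check.** Patients were classified at month 3 among those still progression-free, and time was counted from there. Both groups then agree with the true month-3-to-12 value (77.8% or 56.1%) to within about 1 point, which is simulation noise.

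**Not sized.** Survival, and splits by duration, discontinuation, best response or later therapy, were not simulated.

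**The case against.** The strongest reply is that no biased analysis is actually planned. Table 1 assigns roles to rows, not to items, and starting dose alone could justify the label. Section 8.8 ties none of its stratifications to PFS or survival, and the responder split may only compare characteristics. Detailed methods belong to a SAP that may already set a rule. The study has no comparator and no tests, and TTP/PFS is exploratory.

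Most of this stands, and it limits the point. A reader might infer that the protocol schedules PFS or survival by dose change, or that its main results are biased. The documents support neither. What remains is that Table 1 names post-start items as sub-group identifiers, reports time-to-event outcomes within subgroups, and gives the SAP no boundary. Progression-free proportions and 1- and 2-year survival are also primary objectives, not exploratory ones. The minimum follow-up does not act as a safeguard, because it governs eligibility and neither classifies patients at that time nor restarts the clock.

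It is also fair to object that the sizes rest on assumed inputs, and that the 10.8-month median comes from patients whose disease relapsed or progressed during endocrine therapy, not from a first-line cohort as such. A reader might pair that median with Argentina's 43.6-month window and obtain about 38 points. That is not supported: 43.6 months follows from the letrozole date, whereas the fulvestrant date gives 35.5 months and about 35 to 36 points.

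**Conclusion.** The point holds as a minor, conditional weakness. If Table 1 is followed for progression-free, TTP/PFS or survival results, splits by dose change, interruption or delay would show a false advantage for patients with the event. Splits by duration, discontinuation or later therapy would be distorted by reverse causation, possibly in the other direction. In the main scenarios the false 12-month gap for dose changes is about 4 to 31 points (24.8-month median) or 6 to 36 points (10.8-month median). This rests on exponential PFS, no true effect, and assumed share and timing of changes. The direction for dose changes was the same in every scenario run, but the size is not known for this study. Overall estimates and subgroups known at start, such as starting dose, combination partner and country, are unaffected. The mechanism is certain; whether such splits would be run is not.

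**What to change.** Amend Table 1 and section 8.8, and carry the rule into the SAP:

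1. Limit subgroups for progression-free, TTP/PFS and survival results to variables known at palbociclib start.
2. From the palbociclib row, keep starting dose as an outcome sub-group identifier. Add combination partner explicitly, since the row's definition does not list it. Keep the other items as descriptive exposure results.
3. For outcome subgroups, use only the part of advanced treatment history that precedes palbociclib start. In a first-line cohort little will remain, and the text should say so.
4. Do not report PFS or survival from treatment start by treatment duration, discontinuation or best response.
5. If dose change, interruption or response is examined against these outcomes, use a month-3 landmark, which lies within the minimum follow-up for both partners. Classify patients still progression-free (still alive, for survival), count time from month 3, and do so only where event dates exist.

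**Cost.** Items 1 to 4 need little extra work and lose no patients. The optional landmark drops patients with an earlier event: 1 − 2^(−3/24.8) = 8.0%, or 68 of 847 (647 + 200), at the longer median; 1 − 2^(−3/10.8) = 17.5%, or 148 of 847, if all had the shorter one. It also ignores later changes: if these are spread evenly over months 1 to 8 or 1 to 12, only 2/7 = 29% or 2/11 = 18% fall by month 3. For the 647 records (76% of 847) already collected and reported in 2019, the rule would be applied post hoc in the final all-market report and should be described as such.
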